The study may be terminated at any point at the discretion of the sponsor.

Individual Stopping Rules

No individual dose stopping rules will be implemented.

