6.2.3 Hepatotoxicity Stopping and Rechallenge Rules

Refer to Section [11.7](#) for details regarding drug-induced liver injury guidelines, as specified in the *Guidance for Industry Drug-Induced Liver Injury: Premarketing Clinical Evaluation, July 2009*.

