8.2.2.2 Suicidal Risk Monitoring

Baseline assessment of suicidal ideation and behavior, and treatment-emergent suicidal ideation and behavior will be monitored during the study using C-SSRS and Patient PHQ-9. The C-SSRS is a clinician rating of suicidal behavior and ideation. The

C-SSRS consists of a maximum of 20 items. Columbia Suicide Severity Rating Scale will be administered in study subjects at each study visit to assess possible suicidal ideation and behavior. Reports of suicidal ideation with intent to act (endorse item 4 or 5) and reports of actual, aborted, or interrupted suicide attempts or a behavior preparatory for making an attempt indicate subjects at high risk for suicide. If such reports are identified, the investigator is to appropriately manage the subject in accordance with standard of care. AMG 133 will be discontinued in subject who experience signs of suicidal ideation or behavior. Refer to Sections [11.8](#) through [Section 11.10](#) for more information on mental health monitoring.

8.2.2.3 [Electrocardiograms](#)

Subject must be in supine position in a rested and calm state for at least 5 minutes before ECG assessment is conducted. If the subject is unable to be in the supine position, the subject should be in most recumbent position as possible. The ECGs should be performed in a standardized method, in triplicate, and run consecutively (all 3 ECGs should be completed within a total of 5 minutes from the start of the first to the completion of the third), before blood draws or other invasive procedures. Each ECG must include the following measurements: QRS, QT, QTc, RR, and PR intervals.

As required per Section [1.3](#):

- Single ECG at Screening
- 3 baseline ECGs collected \geq 30 minutes apart, with each baseline ECG in triplicate run consecutively (all 3 ECGs should be completed within a total of 5 minutes from the start of the first to the completion of the third) (total 9 ECGs)
- Triplicate ECGs at time points after dosing

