- While pregnancy itself is not considered to be an adverse event or serious adverse event, any pregnancy complication or report of a congenital anomaly or developmental delay, fetal death, or suspected adverse reactions in the neonate will be reported as an adverse event or serious adverse event. Note that an elective termination with no information on a fetal congenital malformation or maternal complication is generally not considered an adverse event, but still must be reported to Amgen as a pregnancy exposure case.
- If the outcome of the pregnancy meets a criterion for immediate classification as a serious adverse event (eg, female subject experiences a spontaneous abortion, stillbirth, or neonatal death or there is a fetal or neonatal congenital anomaly) the investigator will report the event as a serious adverse event.
- Any serious adverse event occurring as a result of a poststudy pregnancy which is considered reasonably related to the study treatment by the investigator, will be reported to Amgen Global Patient Safety as described in Section 11.4. While the investigator is not obligated to actively seek this information in former study subjects, he or she may learn of a serious adverse event through spontaneous reporting.
- Any female subject who becomes pregnant while participating will discontinue study treatment (see Section 7.1 for details).

Male Subjects With Partners Who Become Pregnant

- In the event a male subject fathers a child during treatment, and for an additional 5 months after discontinuing protocol-required therapies, the information will be recorded on the Pregnancy Notification Form. The form (see Figure 11-2) must be submitted to Amgen Global Patient Safety within 24 hours of the site's awareness of the pregnancy. (Note: Sites are not required to provide any information on the Pregnancy Notification Form that violates the country or regions local privacy laws).
- The investigator will attempt to obtain a signed authorization for release of pregnancy and infant health information directly from the pregnant female partner to obtain additional pregnancy information.
- After obtaining the female partner's signed authorization for release of pregnancy and infant health information, the investigator will collect pregnancy outcome and infant health information on the pregnant partner and her baby and complete the pregnancy questionnaires. This information will be forwarded to Amgen Global Patient Safety.

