The sponsor is the exclusive owner of any data, discoveries, or derivative materials from the sample materials and is responsible for the destruction of the sample(s) at the request of the subject through the investigator, at the end of the storage period, or as

appropriate (eg, the scientific rationale for experimentation with a certain sample type no longer justifies keeping the sample). If a commercial product is developed from this research project, the sponsor owns the commercial product. The subject has no commercial rights to such product and has no commercial rights to the data, information, discoveries, or derivative materials gained or produced from the sample.

See Section [11.3](#) for subject confidentiality.

11.7 Appendix 7. Hepatotoxicity Stopping Rules: Suggested Actions and Follow-up Assessments and Study Treatment Rechallenge Guidelines

Subjects with abnormal hepatic laboratory values (ie, alkaline phosphatase [ALP], aspartate aminotransferase [AST], alanine aminotransferase [ALT], total bilirubin [TBL]) and/or international normalized ratio (INR), and/or signs/symptoms of hepatitis (as described below) may meet the criteria for withholding or permanent discontinuation of Amgen investigational product or other protocol-required therapies, as specified in the *Guidance for Industry Drug-Induced Liver Injury: Premarketing Clinical Evaluation, July 2009*.

Criteria for Withholding and/or Permanent Discontinuation of Amgen Investigational Product and Other Protocol-required Therapies Due to Potential Hepatotoxicity

The following stopping and/or withholding rules apply to subjects for whom another cause of their changes in liver biomarkers (TBL, INR, and transaminases) has not been identified.

Important alternative causes for elevated AST/ALT and/or TBL values include, but are not limited to:

- Hepatobiliary tract disease
- Viral hepatitis (eg, hepatitis A/B/C/D/E, Epstein-Barr Virus, cytomegalovirus, herpes simplex virus, varicella, toxoplasmosis, and parvovirus)
- Right sided heart failure, hypotension or any cause of hypoxia to the liver causing ischemia
- Exposure to hepatotoxic agents/drugs or hepatotoxins, including herbal and dietary supplements, plants and mushrooms
- Heritable disorders causing impaired glucuronidation (eg, Gilbert's syndrome, Crigler-Najjar syndrome) and drugs that inhibit bilirubin (BIL) glucuronidation (eg, indinavir, atazanavir)
- Alpha-1 antitrypsin deficiency
- Alcoholic hepatitis
- Autoimmune hepatitis

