- Wilson's disease and hemochromatosis
- Nonalcoholic fatty liver disease including steatohepatitis
- Non-hepatic causes (eg, rhabdomylosis, hemolysis)

If investigational product(s) is/are withheld, the subject is to be followed for possible drug-induced liver injury (DILI) according to recommendations in the last section of this appendix.

Rechallenge may be considered if an alternative cause for impaired liver tests (ALT, AST, ALP) and/or elevated TBL, is discovered and the laboratory abnormalities resolve to normal or baseline (see next section in this appendix).

Table 13. Conditions for Withholding and/or Permanent Discontinuation of Amgen Investigational Product and Other Protocol-required Therapies due to Potential Hepatotoxicity

Analyte	Temporary Withholding	Permanent Discontinuation
TBL	> 3x ULN at any time	> 2x ULN OR
INR	--	> 1.5x (for subjects not on anticoagulation therapy) AND
AST/ALT	> 8x ULN at any time > 5x ULN but < 8x ULN for \geq 2 weeks > 5x ULN but < 8x ULN and unable to adhere to enhanced monitoring schedule > 3x ULN with clinical signs or symptoms that are consistent with hepatitis (such as right upper quadrant pain/tenderness, fever, nausea, vomiting, and jaundice)	In the presence of no important alternative causes for elevated AST/ALT and/or TBL values > 3x ULN (when baseline was < ULN)
ALP	OR > 8x ULN at any time	--

ALP = alkaline phosphatase; ALT = alanine aminotransferase; AST = aspartate aminotransferase;
INR = international normalized ratio; TBL = total bilirubin; ULN = upper limit of normal

Permanent withholding criteria are met when AST/ALT > 3x ULN in the presence of no important alternative causes for elevated AST/ALT and/or TBL values AND 1 of the following 2 are met: TBL > 2X ULN OR > 1.5x (for subjects not on anticoagulation therapy).

Criteria for Rechallenge of Amgen Investigational Product and Other Protocol-required Therapies After Potential Hepatotoxicity

The decision to rechallenge the subject is to be discussed and agreed upon unanimously by the subject, investigator, and Amgen.

If signs or symptoms recur with rechallenge, then AMG 133 is to be permanently discontinued. Subjects who clearly meet the criteria for permanent discontinuation (as described in [Table 13](#)) are never to be rechallenged.

Drug-induced Liver Injury Reporting and Additional Assessments

Reporting

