- Symptoms (if applicable) including right upper quadrant pain, hypersensitivity-type reactions, fatigue, nausea, vomiting and fever
- Prior and/or concurrent use of alcohol, recreational drugs and special diets
- Concomitant use of medications (including nonprescription medicines and herbal and dietary supplements), plants, and mushrooms
- Viral serologies
- Creatine phosphokinase, haptoglobin, lactate dehydrogenase and peripheral blood smear
- Appropriate liver imaging if clinically indicated
- Appropriate blood sampling for pharmacokinetic analysis if this has not already been collected
- Hepatology consult (liver biopsy may be considered in consultation with a hepatologist)

Follow the subject and the laboratory tests (ALT, AST, TBL, INR) until all laboratory abnormalities return to baseline or normal or considered stable by the investigator. The "close observation period" is to continue for a minimum of 4 weeks after discontinuation of all investigational product(s) and protocol-required therapies.

The potential DILI event and additional information such as medical history, concomitant medications and laboratory results must be captured in the corresponding CRFs.

11.8 Appendix 8. Mental Health Criteria Stopping Rules: Suggested Actions and Follow-up Assessments

Subjects with an increase in score on either the Patient Health Questionnaire 9 (PHQ-9) and/or C-SSRS assessments may meet the criteria for permanent discontinuation of Amgen investigational product or other protocol-required therapies.

Criteria for Withholding and/or Permanent Discontinuation of Amgen Investigational Product and Other Protocol-required Therapies Due to Potential Mental Health Changes

The following stopping rules apply to subjects for whom an increase in their PHQ-9 and/or C-SSRS scores have been identified.

Table 14. Conditions for Permanent Discontinuation of Amgen Investigational Product and Other Protocol-required Therapies Due to Changes in Mental Health Scores

Mental Health Assessment	Permanent Discontinuation
PHQ-9	≥ 10
C-SSRS	OR Answers yes to any items #1-5

PHQ-9 = Patient Health Questionnaire 9 ; C-SSRS = Columbia Suicide Severity Rating Scale

Reporting

To facilitate appropriate monitoring for signals of mental health changes according to the criteria specified in the above, require the following:

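### Protocol Section 6.2.1 says there are no individual dose stopping rules, but Section 8.2.2.2 and Appendices 5, 7 and 8 contain subject-level discontinuation rules; the texts must be reconciled

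*Protocol*

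**What the plan says.** Section 6.2.1 of the protocol deals with cohort escalation, de-escalation and stopping. After Table 11, under a separate heading on individual stopping rules, it states: "No individual dose stopping rules will be implemented".

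Elsewhere the protocol sets rules that act on the individual subject:

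- Section 8.2.2.2: "AMG 133 will be discontinued in subject who experience signs of suicidal ideation or behavior".
- Appendix 7 (Section 11.7): "The following stopping and/or withholding rules apply to subjects for whom another cause of their changes in liver biomarkers" has not been found. Table 13 then gives criteria for temporary withholding and for permanent discontinuation. The text below the table adds "Permanent withholding criteria are met when AST/ALT > 3x ULN in the presence of no important alternative causes" and a bilirubin or INR criterion is also met. On rechallenge it says "If signs or symptoms recur with rechallenge, then AMG 133 is to be permanently discontinued".
- Appendix 8 (Section 11.8): "The following stopping rules apply to subjects for whom an increase in their PHQ-9 and/or C-SSRS scores have been identified". Table 14 lists a PHQ-9 score of 10 or more, or a yes to any of C-SSRS items 1 to 5, under permanent discontinuation.
- Appendix 5 (Section 11.5): "Any female subject who becomes pregnant while participating will discontinue study treatment". A parallel statement covers breastfeeding.

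**The concern.** Section 6.2 is where site staff would look to learn when dosing changes or stops. Its one sentence on individual rules says there are none, while four other places say there are some. A protocol should not leave staff to decide which text governs, least of all on a safety rule.

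There is also a reporting side. Adverse events leading to withdrawal from investigational product are tabulated under the primary safety endpoint (protocol Section 9.4.2.3.1; SAP Table 9-1). That count reads most cleanly if every site applies the same discontinuation rules.

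**Working it through.** The plan gives no figure to reproduce here. The check is a comparison of texts, followed by a count of where the conflict can arise.

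**1. Do the texts conflict?**

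| Place | Acts on | Direction | Referenced within Section 6.2? |
|---|---|---|---|
| 6.2.1, individual stopping rules | individual subject | none implemented | is the statement itself |
| 8.2.2.2 | individual subject | discontinue | no |
| Appendix 7, Table 13 | individual subject | withhold or permanently discontinue | yes, by "6.2.3 Hepatotoxicity Stopping and Rechallenge Rules" |
| Appendix 8, Table 14 | individual subject | permanently discontinue | no |
| Appendix 5 | individual subject | discontinue for pregnancy or breastfeeding | no |

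The first row cannot be literally true together with any of the others.

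**2. Does neighbouring text resolve it?** Section 6.2.2 has withholding and permanent discontinuation in its title, but its content says only that the reason for a dose change is recorded. Section 6.2.3 refers to the liver appendix alone. Section 7.1 lists possible reasons for stopping, including adverse event and pregnancy, but cites neither Table 13 nor Table 14. So within Section 6.2 the liver rules can be found and the mental-health rules cannot.

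**3. How firm are the conflicting rules?** Section 8.2.2.2 is plainly directive, and so is Appendix 5. Appendices 7 and 8 are mixed. Both titles describe the actions as suggested, and both open by saying that subjects may meet the criteria. Their operative text is firmer: both say that the rules apply to the subjects concerned, and Appendix 7 bars rechallenge for subjects who clearly meet the permanent criteria.

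**4. Where can it have effect?** Only at a dose after the first.

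- Part A: one dose, so 0 later doses.
- Part B: days 1, 29 and 57, so 3 − 1 = 2 later doses per subject.
- Cohort 12: days 1, 8, 15 and 43 (note to Table 5), so 4 − 1 = 3.
- Cohort 13: days 1, 8, 15, 22, 29 and 57 (note to Table 6), so 6 − 1 = 5.

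At the planned ceiling of 6 subjects per Part C cohort, that is 6 × 3 + 6 × 5 = 18 + 30 = 48 later-dose occasions. In Part C the C-SSRS and PHQ-9 are predose assessments on dosing days (Tables 5 and 6), so a Table 14 result can be in hand just before a dose.

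Part B is planned at up to 44 subjects, of whom up to 6 + 5 = 11 are on placebo. Section 2.2.2.4 reports that 39 subjects had already been enrolled and had received 1 to 3 doses by the December 2021 data. Under the current amendment, the forward effect therefore falls mainly on Part C.

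**The case against.** The best defence is context. The sentence speaks of dose stopping rules and stands in a section about cohorts, directly after Table 11. The same section says that dose-level recommendations are made per cohort and not per individual. Read that way, it says only that Table 11 has no subject-level counterpart, and it does not touch the liver, mental-health or pregnancy rules. This is plausible and may well be what was meant. It is not what is written: the heading is unqualified, the sentence states no limit, and nothing at that point refers to the other rules.

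The second defence is that specific rules would normally prevail over one general sentence. Section 6.2.3 points to the liver rules, and Section 8.2.2.2 points staff who administer the scales to Appendices 8 to 10. This carries weight for practical risk. A reader might infer that sites are likely to re-dose subjects who meet Table 13 or Table 14. The documents do not support that; they show an ambiguity that a site could misread, and give no evidence that one did or would.

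A reader might also infer that every conflicting rule is mandatory. That is clear for Section 8.2.2.2 and Appendix 5, but the softer titles and openings of Appendices 7 and 8 prevent saying it of them without qualification. The rules on pregnancy and breastfeeding belong in the comparison for completeness, but inclusion criterion 107 admits only women of nonreproductive potential, so they should rarely be invoked.

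**Conclusion.** The contradiction holds on the text. Section 6.2.1 denies, without limit, something that Section 8.2.2.2 and Appendices 5, 7 and 8 provide. It is an internal inconsistency in a safety rule, wrong as written, of minor to moderate severity.

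Its reach is limited. It is inert in Part A and largely past for Part B, so it is live mainly in Part C, at 3 later doses per cohort 12 subject and 5 per cohort 13 subject. These are planned counts of occasions. They do not say how often a subject would meet a criterion, and the documents give no rate for that.

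A reader might go further and conclude that the primary safety analysis is distorted. The documents do not show this. The withdrawal table is one descriptive summary among several, no hypothesis is tested, and SAP Section 9.2 separately summarises discontinuations of investigational product with reasons. Uneven application could shift the table: in a cohort with 6 active subjects, one subject is 1/6 = 16.7%. That is a possibility, not a finding. No sample size or estimate changes.

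The conclusion assumes that the sentence is read as printed. If the sponsor confirms the narrower meaning, what remains is a drafting fault with the same remedy.

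**What to change.** The sponsor must reconcile the Section 6.2.1 sentence with Sections 6.2.3 and 8.2.2.2 and Appendices 5, 7 and 8, and decide which text governs. Two editorial routes are open: remove the sentence, or limit it to what was intended and cross-reference the existing subject-level rules. Whichever is chosen, Section 6.2 should refer to Section 8.2.2.2 and Appendix 8, which it does not do now. No clinical rule is proposed here.

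The cost is about one sentence plus cross-references in a protocol amendment. The SAP needs no change, and no sample size or analysis has to be redone.

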6.2.2 Dosage Adjustments, Delays, Rules for Withholding or Restarting, Permanent Discontinuation

6.2.2.1 Amgen Investigational Product: AMG 133

The reason for dose change of AMG 133/placebo is to be recorded on each subject's CRF(s).

6.2.3 Hepatotoxicity Stopping and Rechallenge Rules

Refer to Section [11.7](#) for details regarding drug-induced liver injury guidelines, as specified in the *Guidance for Industry Drug-Induced Liver Injury: Premarketing Clinical Evaluation, July 2009*.

6.3 Preparation/Handling/Storage/Accountability

Guidance and information on preparation, handling, storage, accountability, destruction, or return of the investigational product and other protocol-required therapies during the study are provided in the IPIM.

6.4 Measures to Minimize Bias: Randomization and Blinding

6.4.1 Method of Treatment Assignment

Subjects will be randomized in a 3:1 allocation ratio, to AMG 133 to placebo, respectively, in double-blind manner **in Part A and Part B cohorts 1 to 11 only. Part C cohorts 12 to 13 is an open-label study.**

The randomization will be performed by IRT.

Subjects will be assigned a randomization number based in sequential order in which they qualified to be randomized. Subjects will be considered randomized once a unique subject randomization number has been assigned.

The randomization date is to be documented in the subject's medical record and on the enrollment CRF.

